- c. UPIRSO's involve a greater risk of harm (including physical, psychological, economic, or social harm) than was previously known or recognized or approved by the IRB.

6. Plan for reporting AEs, SAEs, and UPIRSOs to the IRBs, the CAP Coordinating Center, the Human Research Protections Office (HRPO), and the Data Management Committee (DMC)

The investigator is responsible to monitor safety and record the results of that monitoring in the form of an Adverse Events (AE log). The principal investigator (or designated medical co-investigator) will conduct a review of all AEs upon completion of every study subject and will evaluate the frequency and severity of the adverse events, in order to determine if modifications are required to the protocol or consent forms.

The investigators will report AE's, SAE's, and UPIRSOs to their respective IRBs according to local policies and reporting procedures.

As part of the CAP, additional reporting requirements to the DMC, other IRBs with jurisdiction, and HRPO will be fulfilled by the CAP Coordinating Center Regulatory Coordinator.

VI. Informed consent: A waiver of written informed consent and HIPAA authorization is requested for a pre-screening phone interview and medical record review. Following the phone screen, if an individual appears to meet enrollment criteria and is interested in participating, the subject is invited for a face-to-face interview and the written informed consent and HIPAA authorization is obtained by one of the project investigators. A release of information may be obtained for review of any available historical and clinical data. A written authorization form is obtained from each subject, permitting the research team to use, create, or disclose the subject's PHI for research purposes. PHI that may be collected as part of this study includes participants' name, address, contact information, Social Security Number, Date of Birth, VA/DoD Medical Record Numbers, and dates of study visits. The nature of the project, procedures, relative risks and benefits, and alternatives to participation in the project are discussed with the individual. Following this discussion, the individual is given a copy of the consent form to review at their leisure, and any questions are answered.

If the individual is interested in the project, written informed consent is obtained, and medical and psychiatric screening procedures are undertaken to confirm eligibility. A copy of the consent form is provided to all participants. If the individual decides not to participate in this study, the decision not to participate does not affect eligibility to participate in future studies, to receive treatment at each site or any affiliated facility or to receive treatment on a private basis from a referring clinician.

VI. Confidentiality: Reports generated from this study will not contain any identifying information about the participants. Research records are coded only by a number, and are stored in locked cabinets. Consent forms, HIPAA forms, enrollment logs and release of information forms will be kept locked in a place separate from subject data collection forms. Finally, subjects will be informed that a hard copy of the consent form will be placed in their paper record.

VIII. Location of Study: This study will be conducted at two sites, the West Haven, CT VACHS and the San Antonio Military Medical Center (SAMMC) through its affiliation with the CAP at the University of Texas Health Sciences Center located in San Antonio, TX.

IX. Source of Funding: VA and DoD (W81XWH-13-2-0065 to the University of Texas Health Science Center and a subcontract to Yale University) through the Consortium to Alleviate PTSD (CAP).

X. Probable duration: The study will be conducted over 5 years.

References:

- 1 Brady, K. *et al.* Efficacy and safety of sertraline treatment of posttraumatic stress disorder: a randomized controlled trial. *JAMA* **283**, 1837-1844 (2000).
- 2 Davidson, J. R., Landerman, L. R., Farfel, G. M. & Clary, C. M. Characterizing the effects of sertraline in post-traumatic stress disorder. *Psychol Med* **32**, 661-670 (2002).
- 3 Tucker, P. *et al.* Paroxetine in the treatment of chronic posttraumatic stress disorder: results of a placebo-controlled, flexible-dosage trial. *J Clin Psychiatry* **62**, 860-868 (2001).
- 4 Marshall, R. D., Beebe, K. L., Oldham, M. & Zaninelli, R. Efficacy and safety of paroxetine treatment for chronic PTSD: a fixed-dose, placebo-controlled study. *Am J Psychiatry* **158**, 1982-1988 (2001).

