This is a double-blind, placebo-controlled, 8+ week clinical trial in which patients will be randomized to one of three treatment groups based on the content of their 8 intravenous infusions throughout the study: 0.9% saline (placebo), ketamine (0.2 mg/kg), or ketamine (0.5 mg/kg). On each infusion day, pre-infusion assessment of adverse events and symptom severity will be conducted using a set of clinician- and self-rated scales (see below). Subjects will then receive the ketamine/placebo dose via pump as a 50 mL intravenous infusion administered over 40-minutes based upon randomized treatment assignment. The Research Pharmacy prepares syringes containing 56 mL of drug/placebo (including the 50 mL dose plus 6 mL tubing volume to ensure all the study medication is infused). Possible adverse events (AEs) and mood disturbance symptoms will be assessed repeatedly before, during, and after infusion up to 120 minutes following the study drug administration. At the end of each infusion, clinically significant AEs observed will be recorded in the research record. Subjects will receive 1-2 infusions per week (to assure that no less than 2 calendar days (e.g., Monday & Wednesday; Tuesday & Thursday) and no more than 7 days intervals exist between infusions) for 4+ weeks. A 4-week follow-up period will follow. If an infusion session is missed, it can be made up as long as the 2-day minimum/7-day maximum interval in between sessions is maintained. On each subsequent follow-up visit, possible AE's experienced between visits, will be recorded in the research record. Non-responders (i.e. less than 25% improvement from the baseline CAPS-5 score) at the end of the double-blind treatment period (end of Week 4) will be offered a single infusion of open-label ketamine 0.5 mg/kg. Consistent with the CAP goals, we will collect and bank blood samples at visits 2 (baseline; prior to the first infusion), 3, 7, 11, and 16 for future biomarker analyses.

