SAFTEE	X	X	X	X	X	X	X	X	X	X
VR-12	X		X			X		X	X	X
WHYMPI	X		X			X		X	X	X
Cogstate	X		X			X		X		X
Physical Exam	X									
Medical History	X									
Routine Lab Tests	X									
Breathalyzer	X	X (PRE INF)	X	X (PRE INF)	X (PRE INF)	X	X (PRE INF)	X	X	X
ECG	X									
Serum Pregnancy Test	X									
Urine Pregnancy Test		X (PRE INF)		X (PRE INF)	X (PRE INF)		X (PRE INF)			
Blood Collection/Banking (e.g., DNA, RNA, Plasma, Serum)		X	X		X	X				X
Vital Signs	X	X (PRE,10, 20, 40)	X	X (PRE,10, 20, 40)	X (PRE,10, 20, 40)	X	X (PRE,10, 20, 40)	X	X	X
Infusion		X		X	X					
Open-Label Infusion							X			
IE Blinding Form						X				
Blinding Form						X				

*No study procedures will be completed prior to completion of the Informed Consent. The "Day" number is an approximation and the actual day may vary depending on delays in prior visits.

Test Days

Screening

Informed consent, physical examination and health assessment, ECG, laboratory tests, concomitant medications, MINI psychiatric assessment, and demographic information.

- Measures including, but not limited to, the DVBIC Brief TBI Screen, CAPS-5, PCL-5, MADRS (item 10 only), QIDS-SR, ARAC, CGI, PHQ-9, GAD-7, AUDIT, ISI, PROMIS Sleep, WHYMPI, Pain-NRS, VR-12, Cogstate, QDS will be administered. Refer to Table 2 for the full battery of measures and administration intervals.
- No more than 200 mL of blood will be collected for routine laboratory tests.
- After completing the screening and being deemed eligible for participation in the study, subjects will be randomized.

Infusion session 1 (Day 0)

- Infusions will take place at Biostudies, nursing/medical coverage will be provided by [name] [name] group, and will follow all related hospital and Biostudies standard operating procedures and policies.
- Breath alcohol, and urine pregnancy test;
- Blood collection for the biomarkers banking.
- AE Assessment since last visit;
- Intravenous lines started; Vital signs;
- Measures including, but not limited to, the PCL-5, MADRS, QIDS-SR, ARAC, CGI, GAD-7, PHQ-9, QDS, ISI, and will be completed prior to the study drug administration (refer to Table 2).
- Study drug will be infused over 40 minutes.
- Vital signs will be recorded at approximately 10, 20, and 40 minutes during infusion unless closer monitoring is clinically indicated.
- ARAC, CADSS and PANSS will be completed at 30 and 120 min following the start of the study drug infusion.

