Exploratory aim 1: Safety of repeated ketamine exposure. 1) Changes in psychotic (PANSS), dissociative (CADSS) and cognitive symptoms (Cogstate) across time between groups will be assessed using mixed effects regression models with group as between-subject factor and time as a within-subject factor as described in the primary specific aim. We anticipate significant differences between ketamine and placebo during infusions but no significant between-group differences at discharge and at the two-week and one month follow-up. 2) Descriptive statistics will be calculated for consumption of recreational substances prior to randomization, throughout the trial and for 4 weeks following the last ketamine exposure. If sufficient sample size is available for analytic modeling of recreational substance use between groups, mixed effects models or nonparametric regression will be used to test for differences between groups. 3) Breath alcohol levels over time will be compared as described for Aim 1. 4) Descriptive statistics will be calculated to summarize types and rates of adverse events between groups. Rates of adverse events will be compared using Fisher's exact tests since numbers of adverse events per arm may be small. Exact logistic regression analyses will be used to assess effects of additional potentially confounding covariates on adverse events if possible (i.e. if sufficient numbers of adverse events are present in the sample to allow for such analysis).

Exploratory aim 2: To assess the durability of ketamine effects on PCL-5, we will use mixed effects regression models in the subjects who responded to the study drug by the end of the double-blind treatment. Week post-treatment will be a within-subject factor and the treatment group a between-subject factor in this analysis, and we will covary for severity at the end of treatment. We will perform pairwise comparisons over time to determine if subjects maintain improvements on ketamine during the 4-week follow-up.

Exploratory aim 3: To test the clinical significance of PCL-5 changes, we will perform secondary mixed model analyses on CAPS-5, CGI, VR-12, PROMIS, WHYMPI, and Pain-NRS, using the same approach as described in Aim 1.

Exploratory aim 4: To test the integrity of the blind, we will use chi-square tests and ANOVA models to compare the accuracy and level of confidence in the guessed treatment assignment between groups.

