Ketamine: There are side effects associated with ketamine. Most side effects resolve after stopping the drug. The doses of ketamine proposed for this project (0.2 mg/kg and 0.5mg/kg) have been specifically selected to produce mild to moderate behavioral effects without significant sedation. At these doses, ketamine produces a transient alteration of consciousness including altered sensory processing, and thought processes. Initially, subjects frequently feel “drunk” and giddiness is common. As blood levels increase, blood pressure and heart rate increase moderately. This increase is transient and not considered clinically significant. Subjects report differences in complex problem solving evident on frontal lobe and delayed memory tasks, some subjects may report a narrowing of their concentration, feeling distant from surroundings, and enhanced perception of some sensory stimuli. Subjects sometimes report blurred vision and nystagmus. Alterations in the perception of time, body boundaries, and illusions occur. Subjects may experience visual distortions, altered perception of orientation in space, and inability to control thought processes. Subjects may report feeling quite distanced from their surroundings, describe altered awareness of their bodies, and they may close their eyes. During this period, they are still oriented to time and place. They can complete ratings scales testing memory without impairment, their rate of finger tapping is unchanged and the latency of their response on continuous performance tasks of attention is not increased. However, some individuals feel that they cannot control the experience and find it frightening. Vivid dreams and poor sleep quality after infusion of ketamine has also been reported, although dream content was not necessarily unusual and alterations in sleep were not reported on subsequent nights.

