- We do not view the risks associated with ketamine as minimal.
- Given the established safety and validity of the use of ketamine, we do not view the proposed study as high risk.

Although we have assessed the proposed study as one of moderate risk, the potential exists for anticipated and/or unanticipated adverse events, serious or otherwise, to occur since it is not possible to predict with certainty the absolute risk in any given individual or in advance of first-hand experience with the proposed study methods. Therefore, we provide a plan for monitoring the data and safety of the proposed study on site as follows:

3. Attribution of Adverse Events:

Adverse events (AEs) are defined any untoward, physical, social, economic or psychological occurrence affecting human subjects in research. An AE can be any unfavorable or unintended event including abnormal laboratory finding, symptom, reaction, or disease. An AE does not necessarily have a causal relationship with the research, or any risk associated with the research, the research intervention, or the assessment. Adverse events involve subjects only.

AEs will be monitored for each subject participating in the study. Separate and apart from the determination that an AE has occurred, the site investigators will determine their attribution to the study procedures / design according to the following categories:

- a. **Related:** Adverse event is reasonably regarded as caused by the research.
- b. **Probably:** Adverse event is likely caused by the research.
- c. **Possibly:** Adverse event may be caused by the research.
- d. **Unlikely:** Adverse event is likely not to be caused by the research.

- e. **Unrelated:** Adverse event is clearly not caused by the research

4. Plan for Grading Adverse Events:

The following scale will be used in grading the severity of adverse events noted during the study:

1. Mild adverse event (does not affect patient activity)
2. Moderate adverse event (mild disruption in usual activity)
3. Severe (major disruption in usual activity)

5. Plan for Determining Seriousness of Adverse Events:

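### The rule for recording adverse events at infusions carries an undefined threshold that conflicts with the protocol's own definition, and the source of the counts for the Fisher comparison is not named

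*Protocol*

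**What the plan says.** Protocol section IV.F (Research Plan and Study Procedures) treats assessment and recording differently. On assessment: "Possible adverse events (AEs) and mood disturbance symptoms will be assessed repeatedly before, during, and after infusion up to 120 minutes" after drug administration. On recording at the infusion: "At the end of each infusion, clinically significant AEs observed will be recorded in the research record." On recording afterwards: "On each subsequent follow-up visit, possible AE's experienced between visits, will be recorded in the research record." The threshold in the second statement is not defined anywhere.

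The Data Safety Monitoring Plan, item 3, has no threshold: "An AE can be any unfavorable or unintended event including abnormal laboratory finding, symptom, reaction, or disease." Item 4 grades events as Mild, Moderate or Severe, and item 6 requires an adverse event log.

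In Table 2 the Adverse Events row is marked pre-infusion on every infusion day. The Day 0 procedures, which the later infusion sessions follow, describe that check as "AE Assessment since last visit."

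Exploratory aim 1 plans the analysis: "Rates of adverse events will be compared using Fisher's exact tests since numbers of adverse events per arm may be small." It does not say which record supplies the counts. The SAP contains no adverse-event analysis.

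**The concern.** A mild symptom during an infusion is an adverse event under the Data Safety Monitoring Plan, yet section IV.F does not direct staff to record it. The same symptom reported as occurring between visits would be recorded. The stricter rule therefore falls on the window in which the protocol expects most acute drug effects.

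The protocol also signals in advance that these effects lie below the threshold. Under Potential Risks (Ketamine), it says of the rise in blood pressure and heart rate: "This increase is transient and not considered clinically significant." It goes on to describe infusion reactions, including nausea and vomiting, sedation and headache, as mild and short-lived, with none reaching clinical significance. Staff who follow that wording could reasonably leave them out.

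Safety of repeated exposure is the first secondary aim, and the analysis plan intends to use safety data, together with effect sizes, to inform dose selection for later studies. An adverse-event table built on an undefined judgement made at two sites is a weak basis for either purpose.

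**Working it through.** The documents give no adverse-event rate and no power figure for this comparison, so there is nothing to reproduce. The check is mainly textual.

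1. **Recording rules compared.** Infusion window: clinically significant events, noted at the end of the infusion. Between visits: possible events, no threshold. General definition: any unfavourable or unintended event, with a Mild grade. The first rule is narrower than the other two.

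2. **Does the schedule close the gap?** Not clearly. On infusion days the Adverse Events row has no post-infusion entry. The check at the next visit looks back to the last visit and could pick up events from the previous infusion, but section IV.F directs it at events between visits. Days 1 and 25, about 24 hours after the first and eighth infusions, have both an Adverse Events and a SAFTEE entry. After infusions 2 to 7 the next scheduled check is before the next infusion, and the protocol allows 2 to 7 days between infusions.

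3. **What is captured elsewhere?**
   - CADSS and PANSS are taken at 30 and 120 minutes of every infusion and compared between arms by mixed models (Exploratory aim 1; SAP).
   - Vital signs are taken before infusion and at 10, 20 and 40 minutes; no between-arm analysis is specified.
   - SAFTEE has no threshold and is marked at every visit. Unlike CADSS, PANSS and ARAC it has no time relative to infusion in Table 2, and no analysis of it is stated.

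   The events left exposed are mild acute physical ones.

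4. **Can the effect on the arm difference be sized?** Suppose, purely for illustration, that half of infusion events are recorded, with the same fraction in each arm, and that the Fisher test counts participants with at least one recorded event. The rates of 50% (ketamine) and 20% (placebo) are assumptions; the eight infusions are the protocol's.
   - *One chance per participant to be recorded.* The proportions go from 50% vs 20% to 0.5 × 50% = 25% vs 0.5 × 20% = 10%. The difference falls from 30 to 15 points.
   - *The same 50% and 20% of participants have an event at every infusion, each recorded independently.* The chance of at least one record is 1 − 0.5⁸ = 0.996. The proportions become 49.8% vs 19.9%, and the difference is 29.9 points instead of 30.
   - *Independent risk of 50% or 20% at each infusion.* With full recording: 1 − 0.5⁸ = 99.6% vs 1 − 0.8⁸ = 83.2%, a difference of 16.4 points. With half recorded: 1 − 0.75⁸ = 90.0% vs 1 − 0.9⁸ = 57.0%, a difference of 33.0 points.

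   The same filter can halve the difference, leave it almost unchanged, or double it. Which case applies depends on how events cluster within participants and on the counting unit. The documents give neither.

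**The case against.** The strongest reply is that section IV.F says clinically significant events will be recorded; it does not say milder ones will not be. The Data Safety Monitoring Plan supplies the general definition, monitors every participant and provides a Mild grade. Staff assess events throughout the infusion window and review the day with participants before they leave. SAFTEE probes specific symptoms and documents severity and relationship to drug. On this view the sentence is loose wording and not an exclusion rule.

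Much of that stands, and it limits the point. A reader might infer that nothing below the threshold is captured at infusions, or that the events separating ketamine from placebo are lost. The documents do not support that: the dissociative and psychotomimetic effects are measured and compared between arms whatever the adverse-event rule, and SAFTEE may hold some of the remainder. A reader might also infer that the Fisher comparison is necessarily biased toward no difference. That does not follow either, because the source of the counts is unstated and, with eight infusions, a filter can also widen the participant-level difference.

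The reply does not remove the conflict in the text. Two recording standards remain, one with an undefined term, and the instrument that could make up for it has neither a stated time relative to infusion nor a stated analysis.

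**Conclusion.** The inconsistency is real and should be corrected. Section IV.F and the Data Safety Monitoring Plan give different rules for which events are recorded. Under the narrower rule, mild acute physical events may be missing from the adverse-event record and may be handled differently at the two sites.

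The consequence for the analysis is conditional. The adverse-event rates would be distorted if the Fisher counts come from the section IV.F record without SAFTEE. Neither the size nor the direction of the effect on the arm difference can be determined, because the documents give no event rates, no recorded fraction, no counting unit and no data source. The point does not extend to the CADSS and PANSS comparisons.

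**What to change.** - **Section IV.F:** reconcile it with the Data Safety Monitoring Plan. Record every event that meets the general definition from infusion start to discharge, grade it, and flag it as infusion-window. Keep clinical significance as an additional field.
- **Table 2:** add a post-infusion entry to the Adverse Events row on infusion days, and state when SAFTEE is given relative to the infusion.
- **Exploratory aim 1:** name the data source for the Fisher comparison (log, SAFTEE or both).

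The cost is wording, one table entry, more log lines and a higher reported adverse-event rate. Staff already assess events in this window, so mainly the recording changes. The SAP reports its analyses in the past tense; for data already collected, what remains possible is to name the source of the counts and to state the recording rule beside the adverse-event table.
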